4 STUDY DRUG

Study drug includes both Investigational [Medicinal] Product (IP/IMP) and Non-investigational [Medicinal] Product (Non-IP/Non-IMP) and can consist of the following:

- All products, active or placebo, being tested or used as a comparator in a clinical trial.
- Study required premedication, and
- Other drugs administered as part of the study that are critical to claims of efficacy (eg, background therapy, rescue medications)
- Diagnostic agents: (such as glucose for glucose challenge) given as part of the protocol requirements must also be included in the dosing data collection.

BMS-931699 or a lookalike placebo will be administered weekly as a SC single injection solution. [Table 4-1](#) below indicates the total dose, formulation strength, and number of vials for each treatment arm.

Table 4-1: Treatment Administration

Treatment	Total Daily Dose	Formulation Strength	Number of Vials
1	1.25 mg SC EOW	12.5mg/mL	1
2	5 mg SC EOW	12.5 mg/mL	1
3	12.5 mg SC EOW	12.5mg/mL	1
4	12.5 mg SC Weekly	12.5mg/mL	1
5	Placebo	Placebo	NSS

On Day 1, each subject will receive a single SC dose of either BMS-931699 or placebo.

There are no restrictions related to food and fluid intake associated with BMS-931699 known at this point.

Product description and storage information is described in [Table 4-2](#).

Table 4-2: Study Drugs for BMS-931699

Product Description Class and Dosage Form	Potency	IP/Non-IMP	Blinded or Open Label	Packaging/Appearance	Storage Conditions (per label)
BMS-931699-1* Injection. The composition of the drug product is 12.5 mg/mL BMS-931699 in 20 mM phosphate, pH 5.9, with 5% (w/v) sorbitol.	12.5 mg/mL	IP	Open Label	3 cc vial with 13mm opening, 1-panel, open label. Appearance clear to slightly opalescent, colorless to pale yellow solution, 3 cc vial with 13mm opening, 1-panel, open label. Appearance clear to slightly opalescent, colorless to pale yellow solution, which may contain a few white or translucent particles.	Store refrigerated 2-8°C (36-46 °F). Protect from light, protect from freezing.

* The clinical label will reflect the product name as “BMS-931699-01” to be linked with the product description on the vial.

For study drugs not provided by BMS and obtained commercially by the site or subject, storage should be in accordance with the product label.

Preparation instructions will be provided separately to the site.

4.1 Investigational Product

An investigational product, also known as investigational medicinal product in some regions, is defined a pharmaceutical form of an active substance or placebo being tested or used as a reference in a clinical study, including products already with a marketing authorization but used or assembled (formulated or packaged) differently than the authorized form, or used for an unauthorized indication, or when used to gain further information about the authorized form. The investigational product should be stored in a secure area according to local regulations. It is the responsibility of the investigator to ensure that investigational product is only dispensed to study subjects. The investigational product must be dispensed only from official study sites by authorized personnel according to local regulations.

In this protocol, investigational product is BMS-931699 Injection.

4.2 Non-investigational Product

There are no non-investigational products in this study.

4.3 Storage and Dispensing

The product storage manager should ensure that the study drug is stored in accordance with the environmental conditions (temperature, light, and humidity) as determined by BMS. If concerns regarding the quality or appearance of the study drug arise, the study drug should not be dispensed and contact BMS immediately.

Please refer to section [9.2.2](#) for information on investigation product record retention and Section [4.8](#) for return and destruction instructions.

Study drug not supplied by BMS will be stored in accordance with the package insert.

Investigational product documentation (whether supplied by BMS or not) must be maintained that includes all processes required to ensure drug is accurately administered. This includes documentation of drug storage, administration and, as applicable, storage temperatures, reconstitution, and use of required processes (eg, required diluents, administration sets).

Preparation for Subcutaneous (SC) Use:

For SC dosing, no dilution of the drug product solution (12.5 mg/mL) will be required for doses of 12.5mg. However, doses of 5mg and 1.25mg will require dilution. A commercially available appropriately sized sterile needle and appropriate syringe should be used for withdrawal and administration (refer to the pharmacy reference instruction document for further details on the subcutaneous preparation and administration for materials and instructions, provided separately).

The placebo for BMS-931699 injection is normal saline solution, which is administered in a similar fashion as described for the BMS-931699 injection. Normal saline to use as placebo will not be provided by the Sponsor.

After withdrawal into an appropriate sized syringe, the product must be administered within 4 hours. If not dosed immediately, filled syringes should be kept at 2°- 8° C (36°- 46° F) with protection from light prior to use.

Study personnel will administer the dose to the subject. The primary point of injection should be one of the upper arms; however other points of injections are acceptable. The subjects should be monitored for at least 1 hour after each injection for potential reactions.

4.4 Method of Assigning Subject Identification

Subjects will be randomized to receive either BMS-931699 or placebo according to a computer-generated randomization scheme prepared by a Randomization Coordinator within the Drug Supply Management Department of BMS Research and Development.

During the Screening visit, the investigative site will call into the enrollment option of the Interactive Voice Response System (IVRS) designated by BMS for assignment of a 5-digit subject number that will be unique across all sites. Enrolled subjects, including those not dosed, will be assigned sequential subject numbers starting with 00001, eg, 00001, 00002, 00003.... 00010. The patient identification number (PID) will ultimately be comprised of the site number and subject number. For example, the first subject screened (ie, enrolled) at site number 1, will have a PID of 0001 00001. Once it is determined that the subject meets the eligibility criteria following the Screening visit, the investigative site will call the IVRS to randomize the subject into the treatment period.

4.5 Selection and Timing of Dose for Each Subject

4.5.1 *Double-blind Administration of BMS-931699 or Placebo*

On Day 1, subjects will be randomized to one of the following dosing arms in a 1:1:1:1:1 randomization scheme:

- BMS-931699 at 12.5 mg weekly sub-cutaneous (SC) injection
- BMS-931699 at 12.5 mg every other week (EOW) SC injection
- BMS-931699 at 5 mg EOW SC injection
- BMS-931699 at 1.25 mg EOW SC injection
- Placebo SC injection (short-term period only)

The Pharmacist (or qualified drug preparation person) will know the randomized assignments and will prepare the appropriate dose of active BMS-931699 or placebo accordingly. The prepared drug must be supplied to study personnel in a manner such that neither study personnel nor subjects will be aware of whether they receive active drug or placebo.

Every randomized subject will be required to come to the clinic/research center weekly to be dosed. This will ensure double-blind is maintained despite the variability of regimens. Subjects randomized to weekly subcutaneous injections of either placebo or BMS-931699 will be dosed weekly as per schedule and subjects randomized to one of the every other week arms will be alternating between receiving a subcutaneous injection of BMS-931699 one week and one of placebo the following week.

Every randomized subject will be required to remain on site for at least 1 hour after each dose to ensure safety.

4.5.1.1 Administration Window

A subject's scheduled dosing may be administered within \pm 2 days of the target day to adjust for the subject's and/or the site personnel's convenience.

Refer to Section [4.5.2.1](#) for dose modifications in the presence of an adverse event.

4.5.2 Dose modifications

4.5.2.1 BMS-931699 or Placebo

Dose Modifications in the Absence of Adverse Events

In the absence of adverse events, subjects will complete their scheduled injection as prescribed by protocol. A subject's scheduled dosing may be administered within \pm 2 days of the target day to adjust for the subject's and/or the site personnel's convenience.

- If the study medication cannot be administered within **2** days of the target date, that scheduled dose should be skipped, which means subject will miss one (1) dose. The next dose of study medication should then be administered on the next targeted administration day (\pm 2 days) as originally planned. For example, the Day **15** dose could not be administered until Day **17** and subject comes to the study site to receive it on Day **19**. The planned Day **15** dose should not be given at Day **19** and the next dose will be administered on Day **22** (\pm 2 days). In this example, one missed dose will be reported in the eCRF.

Dose Modifications for Adverse Events

If there is evidence of toxicity (eg, abnormal laboratory tests or clinical adverse events) that, in the judgment of the Investigator, could place the subject at increased risk, study drug administration should be interrupted. Subjects may be considered eligible to receive further study medication treatment only if full resolution of the adverse event is documented, as follows:

- If the adverse event completely resolves and the study medication is administered within **2** days of the target date, the next dose should be administered on the originally planned dosing day with no missed doses.
- If the adverse event completely resolves but study medication cannot be administered within **2** days of the target date, that scheduled dose should be skipped (which means subject will miss one (1) dose). The next dose of study medication should then be administered on the next targeted administration day as originally planned (\pm 2 days). For example, the Day **15** dose could not be administered until Day **17** and adverse event resolution occurs on Day **19**. The planned Day **15** dose should not be given at Day **19** and the next dose will be administered on Day **22** (\pm 2 days). In this example, one missed dose will be reported in the eCRF.

4.5.3 Corticosteroids (Prednisone or Prednisone Equivalent) Dosing

- Prior to Randomization: Corticosteroids (prednisone or prednisone equivalent; refer to Appendix 1) may be used in accordance with the Investigator's clinical judgment and best standard of care. A maximum daily dose of 30mg/day is acceptable to be eligible for the

study and start screening; however, daily dose must be tapered down to a maximum of 10mg/day for at least 5 days prior to Day 1 (randomization day).

- Study Day 1 (randomization day): subjects requiring the use of prednisone (or prednisone equivalent) will be on a maximum dose of 10mg/day.
- Post Day 1 (after initiation of study therapy):
 - For subjects who flare or need to increase their prednisone (or prednisone equivalent) to control disease activity a one-time increase of up to a maximum daily dose of 20 mg/day for up to 2 consecutive days will be allowed to transiently manage disease activity.
 - A subject who requires a total daily dose of prednisone (or prednisone equivalent) exceeding 20 mg/day or who has another flare after the first rescue therapy, will be considered a treatment failure.
 - A subject who meets the treatment failure criteria as described above may continue on study medication; however, a subject requiring more than 20 mg/day of prednisone (or prednisone equivalent) for more than 7 days in the short-term period, or more than 14 days in the long-term extension period, will be discontinued.

Tapering of steroids during the course of the study is encouraged and should be evaluated at all visits. Once subject has received the first dose of study drug, prednisone (or prednisone-equivalent) may be tapered down at the discretion of the Investigator.

4.5.4 *Rescue Therapy*

4.5.4.1 *Short- Term Period*

A one-time increase of up to a maximum daily dose of 20 mg/day for up to 2 consecutive days will be allowed to transiently manage disease activity and will not be considered a treatment failure.

- A subject who requires a total daily dose of prednisone (or prednisone equivalent) exceeding 20 mg/day or who has another flare after the first rescue therapy, will be considered a treatment failure.
- A subject who meets the treatment failure criteria based on prednisone use may continue on study medication; however, a subject requiring more than 20 mg/day of prednisone (or prednisone equivalent) for more than 7 days in the short-term period, will be discontinued.

The use of rescue therapies other than prednisone (or prednisone equivalent), such as cyclophosphamide, any intravenous, any intra-articular or biologic agent is prohibited.

Any changes to or new concomitant therapies must be recorded on the CRF.

4.5.4.2 *Long-Term Extension Period*

The class and dose of background therapies is recommended to remain the same as in the short term period. However, temporary rescue therapy with prednisone (or prednisone equivalent) to transiently manage SLE disease activity may be instituted. The increase in prednisone should not

exceed a total daily dose of 20 mg, and must return to the previous stable dose within 14 days. Subjects requiring more than 20 mg/day for more than 14 days of rescue therapy will be discontinued from the LTE.

The use of rescue therapies other than prednisone (or prednisone equivalent), such as cyclophosphamide, any intravenous, any intra-articular or biologic agent remains prohibited during LTE.

Any changes to or new concomitant therapies must be recorded on the CRF.

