1.3 Objectives(s)

1.3.1 Primary Objectives

To compare the proportion of patients who achieve BICLA response (BICLA response rate) at Day 169.

BICLA is defined as:

- British Isle Lupus Assessment Group improvement, defined as BILAG As at Baseline improved to B/C/D, and BILAG Bs at baseline improved to C/D, and no BILAG worsening in other BILAG organ systems such that there are no new BILAG As or greater than 1 new BILAG B; and
- No worsening in the SLEDAI-2K total score compared to Baseline (defined as no increase in SLEDAI total score); and
- No worsening in the physician's global assessment (MDGA) of disease activity ("no worsening" is defined as less than 10% worsening, equivalent to a 10mm increase on a 100mm visual analog scale [VAS]) compared to Baseline.
- No changes in concomitant medications according to the following criteria:
 - No increase of or addition of a new immunosuppressant agent (azathioprine, mycophenolic acid/mycophenolate mofetil, methotrexate, anti-malarial, leflunomide) over baseline levels.
 - No increase in corticosteroid dose above baseline level outside of those allowed per protocol.

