3.4.2 *Other Restrictions and Precautions*

Active SLE and its treatment are associated with increased risk of infection. Subjects should be provided information about the signs of the most common serious infections (eg, pneumonia, sepsis) and must have the knowledge and means to access appropriate medical care.

3.5 *Discontinuation of Subjects following any Treatment with Study Drug*

Subjects MUST discontinue investigational product (and non-investigational product at the discretion of the investigator) for any of the following reasons:

- Subject's request to stop study treatment and/or participation in the study
- Any clinical adverse event (AE), laboratory abnormality or intercurrent illness which, in the opinion of the investigator, indicates that continued participation in the study is not in the best interest of the subject
- Termination of the study by Bristol-Myers Squibb (BMS)
- Loss of ability to freely provide consent through imprisonment or involuntarily incarceration for treatment of either a psychiatric or physical (eg, infectious disease) illness
- Unblinding a subject for any reason (emergency or non-emergency)
- Development of new active manifestations of lupus requiring treatment with any non-protocol approved medications during the study.
- Inability or subject's failure to comply with the protocol requirements.
- Subject who misses more than 3 consecutive weekly doses.
- Pregnancy
- Treated with prednisone (or prednisone equivalent) at a total daily dose exceeding 20 mg and/or for more than 7 days (short-term period) or more than 14 days (long-term extension period).

Patients should discontinue from study, perform End of Treatment and Follow-up Day 42 visits, and receive standard of care according to local guidelines.

In the case of pregnancy, the investigator must immediately notify the BMS Medical Monitor/designee of this event. If any female subject becomes pregnant she will be immediately discontinued from the study.

All subjects who discontinue investigational product should comply with protocol specified follow-up procedures as outlined in Section 5. The only exception to this requirement is when a subject withdraws consent for all study procedures including post-treatment study follow-up or loses the ability to consent freely (ie, is imprisoned or involuntarily incarcerated for the treatment of either a psychiatric or physical illness).

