### **7.11.2 Time to event Analysis**

Time to treatment failure and time to first flare as assessed by new BILAG 2004 index flare definition will be summarized. For those time to event endpoints, if necessary, the point estimate and its 90% confidence interval for the hazard ratio of each active treatment arm versus placebo will be calculated based on the Cox proportional hazards models. In addition, the distribution of time to the occurrence of event will be estimated using Kaplan-Meier method. The analysis will be based on the Efficacy Analysis Population.

Treatment failure is defined as non-protocol treatment i.e., new or increased immunosuppressive treatment or antimalarials; or parenteral corticosteroids; or protocol prohibited dose of oral corticosteroid; or premature discontinuation from study treatment.

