## **8 CONVENTIONS**

### **8.1 Calculations of Key Measures**

#### **8.1.1 Evaluation of BICLA response**

BICLA response is defined based on the following components:

- British Isle Lupus Assessment Group improvement, defined as BILAG ‘A’s at Baseline improved to ‘B’/‘C’/‘D’, and BILAG ‘B’s at baseline improved to ‘C’/‘D’, and no BILAG worsening in other BILAG organ systems such that there are no new BILAG ‘A’s or greater than 1 new BILAG ‘B’; and,
- No worsening in the SLEDAI-2K total score compared to Baseline (defined as no increase in SLEDAI total score); and,
- No worsening in the physician’s global assessment (MDGA) of disease activity (“no worsening” is defined as less than 10% worsening, equivalent to a 10mm increase on a 100mm visual analog scale [VAS]) compared to Baseline; and,
- No changes in concomitant medications according to the following criteria:
  - No increase of or addition of a new immunosuppressant agent (azathioprine, methotrexate, anti-malarial) over baseline levels

- No increase in corticosteroid dose above baseline level outside of those allowed per protocol.

If a subject failed any of the above criteria above, the BICLA response status of the subjects will be set to non-responder.

For the determination of missing BICLA response status, all subjects who prematurely discontinue from the study medication will be imputed as non-responder at all scheduled efficacy visits subsequent to the point of discontinuation.

If any subject has at most one missing component (e.g. MDGA for BICLA) at a given efficacy visit not due to premature discontinuation, the component-wise response status will be imputed based on the following rules.

- If the given visit is not the last scheduled efficacy visit (Day 169), imputation will depend on the observed responses from the immediate previous efficacy visit and the immediate next efficacy visit within 28 days of the current visit date.
- If the given visit is the last scheduled efficacy visit (Day 169), the imputation will depend on the observed responses at the previous 2 consecutive efficacy visits (within 56 days).
- If a subject has response (at component level) at both efficacy visits, the missing response status at current visit will be imputed as responder. Otherwise, response status will be set to non-responder.

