### **8.1.2      *Evaluation of SRI(X)***

In addition to BICLA, a novel endpoint, the SLE Responder Index [SRI] with a modification used as a primary endpoint in the Anifrolumab study, the results of which were presented and published as an abstract at the American College of Rheumatology (ACR) National Meeting in November, 2015. The basic difference between the SRI defined in our protocol and the SRI in the Anifrolumab study is the addition of a fourth component of the endpoint. The original definition of SRI in the protocol does not include the fourth component based on the use of restricted medications.

The use of restricted medications is an important confounding factor when we analyze the endpoints such as BICLA, and SRI(X). Hence an additional component based on the use of restricted medications (same as the 4th component in the definition of BICLA) is deemed necessary to incorporate into the original definition of SRI (X) in the protocol. The modification to the existing definition of SRI is described below.

An SRI(X) [X= 4, 5, 6, and 8] response @ Day T (e.g. T = 85, 169) is defined as:

- a reduction in Day 1 SLEDAI-2K disease activity score of  $\geq X$  points at Day T; and,
- no worsening of disease (defined as an increase of  $\geq 10$ mm on a 100mm VAS from Day 1 as measured by the MDGA up to time T; and,
- no new BILAG-2004 Index 'A' organ system score and no more than one new or worsening BILAG-2004 Index 'B' organ system scores up to time T ; and,
- *No changes in concomitant medications according to the following criteria:*
  - No increase of or addition of a new immunosuppressant agent (azathioprine, methotrexate, anti-malarial) over baseline levels
  - No increase in corticosteroid dose above baseline level outside of those allowed per protocol.

If a subject failed any of the above criteria, the SRI(X) response status of the subjects will be set to non-responder.

For the determination of missing SRI(X) response status, all subjects who prematurely discontinue from the study medication will be imputed as a non-responder at all scheduled efficacy visits subsequent to the point of discontinuation.

If any subject has at most one missing component (e.g. MDGA for SRI(X)) at a given efficacy visit not due to premature discontinuation, the component-wise response status will be imputed based on the following rules.

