## 10 APPENDIX 1 RELEVANT PROTOCOL DEVIATIONS

### Eligibility Deviations:

- Subjects who do not have SLE as defined by meeting 4 of the 11 classification criteria of the American College of Rheumatology for the classification of SLE, either sequentially or coincident at screening

- Subjects who do not have one 'A' in Musculoskeletal or Mucocutaneous body systems or two 'B's in BILAG score (at least one in Musculoskeletal or Mucocutaneous body systems and one in any other body system) at screening
- Elevated ANA<1:80 and anti-dsDNA is not positive and anti-Sm is not positive at screening
- Subjects who have SLEDAI < 6 at screening
- Subjects who receive more than 10mg/day of prednisone (or prednisone equivalent) at randomization day (Day 1)

Incorrect Dosing:

- At least 4 consecutive doses are missed prior to the Day 169 and not discontinued as per protocol

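### SAP 8.1.1 and 8.1.2 leave treatment failure out of the BICLA and SRI(X) scoring rules, so some rescue therapies that the protocol prohibits need not make a subject a Day 169 non-responder

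*Protocol*

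**What the plan says.** **The prohibition.** Protocol 4.5.4.1 (Rescue Therapy, Short-Term Period) reads: "The use of rescue therapies other than prednisone (or prednisone equivalent), such as cyclophosphamide, any intravenous, any intra-articular or biologic agent is prohibited". It attaches no consequence for response status. The prednisone rules just above it do: they say when a subject is a treatment failure.

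**The endpoint in the protocol.** Protocol 5.4.1.1 describes BICLA as BILAG-2004, SLEDAI-2K, the physician's global assessment and the absence of treatment failure. Protocol 1.3.1 gives the medication part as "No increase of or addition of a new immunosuppressant agent (azathioprine, mycophenolic acid/mycophenolate mofetil, methotrexate, anti-malarial, leflunomide) over baseline levels", together with a corticosteroid-dose condition.

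**The endpoint in the SAP.** Section 8.1.1 has two medication tests. The first is "No increase of or addition of a new immunosuppressant agent (azathioprine, methotrexate, anti-malarial) over baseline levels". The second is "No increase in corticosteroid dose above baseline level outside of those allowed per protocol". Section 8.1.2 adds the same component to SRI(X): "an additional component based on the use of restricted medications (same as the 4th component in the definition of BICLA) is deemed necessary".

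**Treatment failure in the SAP.** The definition stands only in 7.11.2 (time-to-event analysis). It starts from non-protocol treatment, names new or increased immunosuppressive or antimalarial treatment, and ends "or parenteral corticosteroids; or protocol prohibited dose of oral corticosteroid; or premature discontinuation from study treatment".

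**Neighbouring rules.** Protocol 3.5 requires study drug to be stopped for, among other reasons, "Development of new active manifestations of lupus requiring treatment with any non-protocol approved medications during the study". SAP 8.1.1 scores subjects who stop study drug as non-responders at later visits. The only deviation after Day 1 in SAP Appendix 1 is "At least 4 consecutive doses are missed prior to the Day 169 and not discontinued as per protocol".

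**The concern.** The protocol and SAP 7.11.2 both treat non-protocol therapy as failure, but the rule that will be programmed for the primary endpoint does not refer to it. A subject could be counted as a treatment failure in the time-to-event analysis and as a BICLA responder in the primary analysis.

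SAP 8.1.2 itself calls use of restricted medication an important confounding factor for BICLA and SRI(X), and SRI(X) was modified for that reason. If prohibited rescue is more common on placebo, which is plausible but not stated in the documents, the resulting false responders gather in the placebo arm and shrink the treatment difference.

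**Working it through.** **Step 1. Run each prohibited rescue through the two tests in SAP 8.1.1.** Assume it is given for worsening of existing disease to a subject who stays on study drug.

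| Rescue prohibited in protocol 4.5.4.1 | Agent-list test | Corticosteroid test | Scored |
|---|---|---|---|
| Intravenous or intra-articular corticosteroid | not named | fails: an increase the protocol does not allow, and the clause has no limit by route | non-responder |
| Cyclophosphamide | depends on whether the bracket is complete | does not apply | unclear |
| Biologic | not named | does not apply | can be a responder |
| Non-steroid intravenous or intra-articular agent | not named | does not apply | can be a responder |

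Two points favour reading the bracket as complete. It has no words such as ‘for example’, and item 15(b) of the Amendment 06 change list treats it as a list to which agents are added. The SAP bracket is also shorter than the protocol's: it lacks mycophenolate and leflunomide.

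A biologic rescue fits the non-protocol treatment of SAP 7.11.2. A non-steroid injection may not fit the items named there, but it is still a prohibited rescue.

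**Step 2. Time scope.** In SAP 8.1.2 the physician's global and BILAG conditions run up to the visit. The medication condition states no period, in 8.1.1 or in 8.1.2.

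**Step 3. Reproduce the plan's power.** Inputs from protocol 8.1 and SAP 5: n = 70 per arm, placebo rate 25%, active rate 50% or 45%, one-sided 0.05, continuity-corrected chi-square.

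With x placebo and y active responders, reject when

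z = [(y − x)/n − 1/n] / √[2p̄(1 − p̄)/n] > 1.645, where p̄ = (x + y)/(2n).

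Power is the sum of Bin(x; 70, p_P) × Bin(y; 70, p_A) over all rejecting pairs. This gives 89.8% for 50% v 25% (stated: at least 89%) and 74.7% for 45% v 25% (stated: 74%). Both stated figures reproduce.

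**Step 4. Add false responders.** One wrongly scored placebo subject adds 1/70 = 1.4 percentage points to the placebo rate. Let f_P and f_A be the shares scored as responders only because prohibited rescue is not counted. The documents give no such rate, so every non-zero share below is an assumption. The rates become 25% + f_P on placebo and 45% + f_A or 50% + f_A on active.

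| f_P / f_A | Rates (20-point case) | Power | Rates (25-point case) | Power |
|---|---|---|---|---|
| 0 / 0 | 25% v 45% | 74.7% | 25% v 50% | 89.8% |
| 2% / 0.5% | 27% v 45.5% | 67.7% | 27% v 50.5% | 85.7% |
| 3% / 1% | 28% v 46% | 65.1% | 28% v 51% | 84.1% |
| 5% / 1% | 30% v 46% | 55.3% | 30% v 51% | 77.2% |
| 5% / 5% | 30% v 50% | 73.3% | 30% v 55% | 89.1% |

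The loss comes from imbalance between the arms. Equal shares cost very little.

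**The case against.** The strongest case against is that other text already removes most of these subjects.

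- **Corticosteroid clause.** Steroid by a prohibited route is an increase outside what the protocol allows. This stands. A reader might infer that an injected steroid for worsening arthritis escapes the endpoint; the clause has no limit by route, so the documents do not support that.
- **Cyclophosphamide is a new immunosuppressant agent.** This is arguable. Nothing says that the bracket is exhaustive, and inclusion criterion 2(c)(vi) recognises immunosuppressives beyond the background list. It stands as an ambiguity.
- **Stopping rules.** Protocol 3.5 requires discontinuation for new manifestations needing non-approved medication, and for failure to comply with the protocol. Such subjects then become non-responders. This stands in part: worsening of existing disease does not clearly meet the first trigger, and whether the second covers rescue given by a physician is a matter of judgment.
- **The protocol already has absence of treatment failure.** True, but SAP 8.1.1 does not carry it over. That mismatch is the point itself, not an answer to it.
- **Text not available.** Protocol 3.4.1 (Prohibited and/or Restricted Treatments) cannot be seen. It may state a consequence, so no claim is made that the whole protocol is silent.
- **Appendix 1.** Deviators are not excluded from any analysis population (SAP 7.2), and the per-protocol analysis is optional once at least 10% of subjects deviate. The gap in that list does not touch the primary analysis. This stands.

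**Conclusion.** The point holds as a mismatch between the protocol's description of BICLA and the SAP's scoring rule, with a narrow practical gap. That gap is a biologic, a non-steroid intravenous or intra-articular agent, or cyclophosphamide if the bracket is complete, given for existing disease to a subject who stays on study drug.

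A reader might infer that any subject given any prohibited rescue can be a responder. The documents do not support that, because the corticosteroid clause and the discontinuation rule catch a good part. The SRI(X) part applies to the SAP definition only, since the protocol's SRI has no medication component.

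The size is unknown. Under the assumed placebo-heavy shares, power falls by 7.0 to 19.4 points for the 20-point effect (74.7% to 67.7% and 55.3%) and by 4.1 to 12.6 points for the 25-point effect (89.8% to 85.7% and 77.2%). These shares are illustrations, not estimates. Equal shares of 5% cost 1.4 points in the 20-point case, and with no such subject the effect is zero. The case for acting rests on the inconsistency and the low cost of removing it, not on these figures.

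**What to change.** In SAP 8.1.1 and 8.1.2, add to the medication component: a subject who, after Day 1, receives for SLE activity any rescue therapy prohibited in protocol 4.5.4.1, or who otherwise meets the treatment-failure definition, is a non-responder at all visits from first use. State that therapy given for other reasons, such as an intravenous antibiotic for infection, is not counted.

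Reconcile this wording, and the two agent lists, with protocol 1.3.1, protocol 5.4.1.1 and SAP 7.11.2, so that one definition of treatment failure serves both the responder endpoints and the time-to-event analysis.

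Optionally, add prohibited SLE rescue to Appendix 1. This affects only the optional per-protocol analysis.

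The cost is a sentence or two in the SAP and one derivation, made before unblinding. Protocol 4.5.4.1 already requires changed or new concomitant therapies to be recorded on the CRF, so no new data item is added; the derivation does need the reason for use to be identifiable. Response rates may fall slightly. This is a scoring rule only and changes nothing about what a patient may be given.
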